**Evaluations**

These evaluation measurements will be administered at the initial research assessment session as well as the final research assessment session, except the K-SADS and WASI which will be only administered at the initial research assessment session. A separate remote visit may be used to conduct K-SADS administration. All of these evaluations are solely performed for research purposes.

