**Initial evaluation:**

Participants and their parent/guardian will complete a diagnostic assessment session following informed consent. This will be held at the outpatient clinic of the department of psychiatry, at University of Nebraska Medical Center. Participants and their parent/guardian will be interviewed using the Schedule for Affective Disorders and Schizophrenia for School-Age Children-Present and Lifetime Version (K-SADS) (Kaufman et al., 1997) to confirm the diagnosis of ADHD/CD/ODD/DMDD, and to rule out any other psychiatric diagnoses listed in the exclusion criteria. K-SADS may be completed remotely by video call or phone. IQ will be measured by the Wechsler Abbreviated Scale of Intelligence, Second Edition (2-subtest form)(Wechsler, 2011). The WASI-II is standardized, well-established test for measurement of intelligence in adolescents population (David Wechsler, 2011). This will be used to rule out intellectual disability (I.Q. < 70)

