**Symptom Profile Assessment:**

The Affective Reactivity Index (ARI) will be completed at the initial research assessment session and the final research assessment session. ARI is a 7 item inventory (self-report

and parent-report versions) specifically designed to measure irritability and emotional dysregulation (Stringaris et al., 2012). This will be used to measure the outcome of improvement in irritability by oxytocin treatment.

The Behavior Assessment System for Children, second version (BASC-3) will be completed at the initial research assessment session and the final research assessment session. BASC-3 is parent-reported, well-established scale for externalizing/internalizing problem of children and adolescents (Reynolds, 2015). This will be used to measure the outcome of improvement in emotional dysregulation and other related symptoms (externalizing behavior) by oxytocin treatment.

The Inventory of Callous Unemotional trait (ICU) will be completed at the initial research assessment session and the final research assessment session. ICU is a 24 item inventory specifically designed to measure callous-unemotional trait in children and adolescents (Berg et al., 2013; Frick, 2004). This will be used to measure outcome of improvement in callous-unemotional trait by oxytocin treatment. This will be also used to assess covariate function of callous-unemotional trait on treatment response.

The Reactive-Proactive Aggression Questionnaire (RPAQ) will be completed at the initial research assessment session and the final research assessment session. RPAQ is a 23 item inventory (self-report) specifically designed to measure two different types of aggressive behavior, i.e., reactive and proactive aggression (Raine et al., 2006). This will be used to measure outcome of improvement in related symptom of aggressive behavior by oxytocin treatment.

The Clinical Global Impression: Severity and Clinical Global Impression: Improvement scales (CGI-S and CGI-I) will be used at study entry and study completion to quantify, based on clinician's global assessment of the individual, the severity of symptoms compared (study entry and completion) and the degree of improvement (study completion) which may or not be attributable to the study intervention. Other symptom profile measurements will be used to assist the clinician in the rating of this measure.

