### **Oxytocin/placebo administration**

If the participants are assigned to the oxytocin treatment arm by randomization, they will be initiated on oxytocin administration after the MRI visit 1 and MEG visit 1. Following previous studies using intranasal oxytocin administration (Dadds et al., 2014; Guastella & MacLeod, 2012; MacDonald et al., 2011), subjects weighing >40kg will receive a total of 24 IU of oxytocin delivered as 2-6 IU puffs to each nostril once daily. Subjects weighing <40kg will receive a total of 12 IU of oxytocin delivered as 1-6 IU puff to each nostril daily. Participants will receive 14 to 21 days of daily oxytocin/placebo administration. After 14 days of oxytocin/placebo administration, participants will be scheduled to have MRI visit 2 and MEG visit 2. After those two visits are completed, participants will stop oxytocin/placebo administration. Participants who are assigned to placebo treatment branch will receive identical bottles and instructions for delivery of all the other ingredients of nasal spray except oxytocin. The instruction and demonstration will be given to the parents or parent/legal guardian as the first administration of the nasal spray done at the clinic by either child and adolescent psychiatrist or advanced practice registered nurse. The daily administration will be done by dispatching either oxytocin or placebo nasal spray to the parents of the participants. The oxytocin and placebo nasal spray will be prepared by the University of Nebraska Medical Center research pharmacist who will be un-blinded to each subject's treatment assignment. The randomization will be done by the department of pharmacology by a computer-programmed randomization procedure.

The participants will have one or two weekly visits to the clinic, depending on the duration of the trial (one if it is 14 days, 2 if it is more than 14 days and less than 21 days). If the participant is having two weekly visits, the first will be conducted by phone. They will be assessed for symptom level, nasal spray tolerance, and assessment of adverse effects. Participants will be initiated on psychiatric treatment if it is indicated by change of their psychiatric condition (such as worsening of psychiatric symptoms). In this case, they will be

withdrawn from the study.

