**Withdrawal Criteria**

1. Initiation of any medication that may have psychotropic effects (newly introduced antidepressants, antipsychotics, anxiolytics, stimulants, and non-stimulant ADHD medications).

2. Discovery of neurologic disorder (including seizures) or anatomical abnormality of brain (including brain neoplasm, hydrocephalus) during participation.
3. Discovery of substance abuse or dependence.
4. Inability of the participant to complete fMRI or MEG due to claustrophobia despite previous questioning.
5. Participants who do not want to continue with the study.
6. Participants who cannot or will not cooperate with study procedures.
7. Participants who experience strong discomfort or develop side effect following the administration of oxytocin or placebo nasal spray.
8. Participants who experience significant worsening of psychiatric symptoms that warrant change of treatment (such as inpatient psychiatric hospitalization).

**G. Describe the specific criteria for halting or early termination of the study (for example statistical evidence of unacceptable toxicity or early demonstration of efficacy or lack of efficacy).**

The study would be halted in followings;

1. Early evidence showing lack of efficacy on irritability or worsening of irritability by oxytocin treatment: After the preliminary phase of the study (10 patients on each arms of oxytocin and placebo trial), if it turns out that children and adolescents experience significant worsening of their psychiatric/behavioral symptoms, or have no change in their psychiatric/behavioral symptoms, we then will consider terminating the study.
2. MEG and/or fMRI become inoperable
3. Serious injury related to procedure (MEG, fMRI, or oxytocin administration) occurs

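### Children who worsen enough to need a change of treatment leave the study with no ARI scheduled, so the primary comparison would tend to omit them for an outcome-related reason

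*Combined protocol and SAP*

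**What the plan says.** **Who leaves.** Section 18.F lists criteria for withdrawing a child from the research. Item 8 covers "Participants who experience significant worsening of psychiatric symptoms that warrant change of treatment (such as inpatient psychiatric hospitalization". Item 1 covers "Initiation of any medication that may have psychotropic effects", whatever the reason. Section 12.B (Oxytocin/placebo administration) says "Participants will be initiated on psychiatric treatment if it is indicated by change of their psychiatric condition (such as worsening of psychiatric symptoms", and adds that such a child is withdrawn from the study.

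**When the ARI is taken.** Under Evaluations: "These evaluation measurements will be administered at the initial research assessment session as well as the final research assessment session". Under Symptom Profile Assessment: "The Affective Reactivity Index (ARI) will be completed at the initial research assessment session and the final research assessment session". Section 12.B places the final assessment with the second fMRI and MEG scans, after 14-21 days of spray. For the weekly contacts it says only "They will be assessed for symptom level, nasal spray tolerance, and assessment of adverse effects"; no instrument is named. Section 18.B allows extra clinic visits and attaches no ARI to them.

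**What is analysed.** Section 4.B makes the primary outcome the ARI change from baseline to the last visit. Section 12.F tests it with a two-sample t-test. The internal-pilot text takes the ARI at baseline and at each patient's last visit and uses the pooled SD of the change to recalculate the sample size. Section 4.A counts 104 completers, 52 per group; section 4.C caps consents at 140. No analysis set or missing-data rule is given.

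**The concern.** A change score needs a second ARI. A child withdrawn before the final session has none scheduled, so following the schedule drops that child from the t-test. The reason for leaving, worsening that warrants other treatment, is closely related to the outcome, irritability. The comparison would then be made mainly among children who did not worsen enough to be removed. Recruiting others until 104 complete restores the number but not the children who worsened.

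If oxytocin works as assumed, more placebo than oxytocin children would leave this way, and the estimated benefit would be too small.

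The gap is wider than the primary outcome. The BASC-3, ICU, RPAQ, CGI and CGAS are repeated at the same final session. The internal-pilot SD would also be computed without the upper tail of change and would tend to be too small.

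**Working it through.** **1. The plan's own figure.** Inputs from section 4.B: means 0 and -4.0, SD 7.2, two-sided 0.05, 52 per group. The exact noncentral t gives n = 51.84, rounded up to 52, and power 80.1% at 52. The stated size reproduces.

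**2. Illustrative model.** The cut-offs and removal shares are assumptions; the documents give no withdrawal rates. Change is normal with SD 7.2. A child whose ARI rises by more than c is withdrawn without an ARI with probability p. There are 52 completers per arm. For an arm with mean μ, let a = (c - μ)/7.2, q = 1 - Φ(a) and f = φ(a). Then:

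- share lost = pq
- retained mean = μ - 7.2·p·f/(1 - pq)
- retained variance = 7.2²·[1 - p(q + a·f)]/(1 - pq) - [7.2·p·f/(1 - pq)]²

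**3. Worked case, c = 7.2, p = 50%.**

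- Placebo: a = 1, q = 0.1587, f = 0.2420. Mean = -7.2 × 0.5 × 0.2420/0.9207 = -0.946; SD 6.64.
- Oxytocin: a = 11.2/7.2 = 1.556, q = 0.0599, f = 0.1190. Mean = -4 - 7.2 × 0.5 × 0.1190/0.9700 = -4.442; SD 6.83.
- Difference = -4.442 + 0.946 = -3.50, which is 12.6% smaller than -4.0.
- Pooled SD = √[(6.64² + 6.83²)/2] = 6.74; power 74.5%.

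**4. Grid.** The last column is explained in step 7.

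| c | p | lost, placebo / oxytocin | difference | pooled SD | power | break-even g |
|---|---|---|---|---|---|---|
| 7.2 | 10% | 1.6% / 0.6% | -3.91 | 7.12 | 79.2% | 9.2 |
| 7.2 | 25% | 4.0% / 1.5% | -3.76 | 6.99 | 77.6% | 9.6 |
| 7.2 | 50% | 7.9% / 3.0% | -3.50 | 6.74 | 74.5% | 10.2 |
| 9 | 10% | 1.1% / 0.35% | -3.92 | 7.13 | 79.3% | 10.9 |
| 9 | 25% | 2.6% / 0.9% | -3.80 | 7.02 | 78.1% | 11.2 |
| 9 | 50% | 5.3% / 1.8% | -3.59 | 6.82 | 75.8% | 11.6 |
| 10.8 | 10% | 0.7% / 0.2% | -3.94 | 7.15 | 79.5% | 12.6 |
| 10.8 | 25% | 1.7% / 0.5% | -3.85 | 7.06 | 78.6% | 12.8 |
| 10.8 | 50% | 3.3% / 1.0% | -3.69 | 6.91 | 77.0% | 13.1 |

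In children, the losses run from about 0.3 to 4 per 52 on placebo and 0.1 to 1.6 per 52 on oxytocin.

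**5. Bounded scale.** If the seven items score 0-2 (assumption), the ARI runs 0-14, and a child entering at 7 or more cannot rise by more than 7. Simulated scores were clipped to 0-14, with entry scores uniform on 4-14 or rounded normal with mean 8 (SD 2.5) or mean 6 (SD 2), held within 4-14. Cut-offs were 7.2 and 9, removal 10% to 50%. Shrinkage was about 0.2% to 9%, largest with low entry scores. Placebo loss at 7.2/50% was about 2.0% to 4.5%. Clipping also lowers the true difference and the SD, so only the relative shrinkage is comparable with step 4.

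**6. Internal-pilot SD.** At 7.2/50%, an expected SD of 6.74 instead of 7.2 gives 46 rather than 52 per group for a difference of 4.0. For scale, the standard error of an SD from 10 per group is about 7.2/√(2 × 18) = 1.2, so the 0.46 shift lies within the pilot's own noise.

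**7. Measuring these children after other treatment.** If that treatment lowers the ARI by g, the difference is -4 + g × (placebo share lost - oxytocin share lost). At 7.2/50% and g = 4 it is -4 + 4 × (0.0793 - 0.0300) = -3.80, against -3.50 when they are omitted. Omission becomes the smaller bias at g = 0.505/0.0493 = 10.2; across the grid the break-even is 9.2 to 13.1.

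**The case against.** **Last visit may already cover it.** The pilot text takes the ARI at each patient's last visit, which could mean a withdrawal visit, and nothing forbids bringing the final assessment forward. This stands as an ambiguity. It is not a provision: the schedule ties the ARI to the final session, no ARI is attached to withdrawal, and no carry-forward rule exists. Equally, a reader might infer that the plan prescribes a completers-only analysis. It does not say so; the omission follows from applying the schedule.

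**The trigger is not the ARI.** Item 8 concerns psychiatric symptoms generally, with hospitalization as its example, over two to three weeks. Withdrawal for other symptoms weakens the link, and few children may qualify. This stands, and it makes the grid an illustration rather than a forecast.

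**The allowance of 140 absorbs losses.** It covers the count, not the selection.

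**False benefit.** A reader might infer an inflated type I error. With no true effect and 25% v 50% of equally worsened children removed by arm, the model gives a false difference of 0.25 to 0.49 points and type I error of 5.4% to 6.5%. The documents suggest no reason for such an imbalance in a double-blind trial.

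**Safety.** A reader might also infer that adverse-effect monitoring is lost. Adverse effects are assessed at each visit and there is an independent DSMB, so the documents do not support that.

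**Conclusion.** The point holds as a low-cost improvement, with medium confidence. Children whose worsening warrants a change of treatment leave the study, and no ARI is scheduled at or after that moment. The direction under the plan's own hypothesis is conservative: the benefit is understated. The size cannot be known from the documents and is probably small. The range of 1.5% to 12.6% shrinkage rests on unbounded normal changes, assumed cut-offs of 7.2 to 10.8, assumed removal of 10% to 50%, and withdrawal driven by ARI rise alone. A bounded 0-14 scale brings it to about 0.2% to 9%. Removing every child above 7.2 would give -2.84 and 66% power, but item 8's wording makes that unlikely. It would also be wrong to confine the point to the primary estimate, because the other final-session scales and the pilot SD depend on the same visit.

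**What to change.** Leave every clinical criterion as it is, and separate stopping spray or scans from leaving the study.

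- For every randomised child who has not withdrawn consent, collect the ARI, in the same informant versions as at baseline, at stopping (without delaying care) and again at the day 14-21 assessment, whether or not the second scans are done. Phone or video can be used if needed; the study already works this way: "If the participant is having two weekly visits, the first will be conducted by phone" and "K-SADS may be completed remotely by video call or phone".
- Define the last visit as the day 14-21 assessment, with the ARI at stopping used when that is missing. State in advance how a child with neither value is handled.
- Analyse all randomised children by assigned arm.
- Add one simple sensitivity analysis giving unfavourable values to children withdrawn for worsening. Do not rely on imputation by withdrawal reason: on the step 4 counts it would rest on about 0.4 to 5.7 children across both arms.

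The cost is a protocol wording change, a few extra 7-item questionnaires (self- and parent-report) and some contacts after stopping. The main downside is that a day 14-21 ARI after other treatment reflects that treatment. In the same illustrative model, leaving the children out is the smaller bias only if that treatment lowers the ARI by more than about 9 points; the ARI at stopping lets this be examined.

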## **CHARACTERISTICS OF THE SUBJECT POPULATION**

### **4. Accrual**

**Is this study conducted solely at sites under the oversight of the Joint Pediatric IRB (e.g. UNMC, TNMC, CH&MC, UNO)?**

Yes

**A. What is the total number of subjects (per group, as applicable) needed to complete the research in order to achieve the scientific objectives of the research?**

104 subjects are needed to complete the trial (52 per treatment group).

**B. What is the statistical or other justification for the total number of subjects needed to complete the research in order to achieve the scientific objectives of the research?**

The primary outcome is the change of Affective Reactivity Index (ARI) from the baseline to the last visit. A sample size of n=52 per group will provide 80% power to detect a difference between the group means of -4.0 in the change of ARI of -4.0 at the significance level of

0.05 using a two-sided two-sample t-test, assuming the mean of -4.0 and the standard deviation of 7.2 in the oxytocin group, and the mean of 0 and the standard deviation of 7.2 in the placebo group.

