#### **Sample size for the internal pilot study**

Given the uncertainty regarding the parameter used to calculate the sample size, an internal pilot study will be conducted to obtain reliable estimate of standard deviation (SD) to recalculate the sample size and assess the retention rate. The minimum size for the internal pilot study,  $n=10$  per group (19% of the pre-planned sample size) will be considered.

---

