### **Statistical methods for the internal pilot study**

The first 20 patients will be enrolled and randomly assigned into placebo and oxytocin group. The primary outcome ARI will be measured at the baseline and last visit for each patient. The change of ARI will be calculated as the measure at the last visit minus the measure at the baseline for each patient. The treatment status of each patient will be labeled as A and B by the third party, and all persons associated with the internal pilot study will be kept blinded for group assignment. The SD of the change of ARI will be estimated for each intervention group, and will be used to compute the pooled SD for the internal pilot study. Recalculation of the sample size will be performed using a two sample independent t-test and the pooled SD. The retention rate will be assessed as well.

The data on genetic polymorphisms and OT-treatment outcomes on the neural and psychological measures will be used primarily as pilot data to advise future larger-scale studies. OXTR SNPs vary in frequency in western populations, but there should be sufficient exemplars of varying genotypes to allow preliminary analyses. For example, a commonly-identified OXTR SNP associated with variation in social behavior (rs53576) occurs in frequencies of 53.5% and 46.5% for the risky genotype (A/A and A/G) relative to resilient genotype (G/G) in a Caucasian sample (Jacob et al., 2007).

Finally, we will simultaneously test all measures (e.g., at baseline) in a multivariate analysis to determine the most important measures for predicting outcome in terms of behavioral change (Ecker et al., 2010). It is hoped that this will show which ones of the variables are the best predictors of treatment response, and which aspects are best influenced by treatment.

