**E. Is there is an independent DSMB for this study?**

Yes

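### Section 18.G makes no change in symptoms at 10 patients per arm a ground to consider ending the trial, with no measure, cut-off or comparison, at a size that cannot exclude the design effect

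*Combined protocol and SAP*

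**What the plan says.** Section 18.G asks for specific halting criteria and offers statistical evidence as an example. The answer opens "The study would be halted in followings". Item 1 is headed "Early evidence showing lack of efficacy on irritability or worsening of irritability by oxytocin treatment" and applies after a preliminary phase of 10 patients on each arm. It has two limbs. One is significant worsening of psychiatric or behavioural symptoms. The other reads "or have no change in their psychiatric/behavioral symptoms, we then will consider terminating the study". Neither limb names a scale, a size of change or a comparison.

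Other sections bear on this:

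- **Section 4.B (internal pilot).** With 10 per group, 19% of the planned sample, "an internal pilot study will be conducted to obtain reliable estimate of standard deviation (SD) to recalculate the sample size" and to assess retention.
- **Section 12.F (internal pilot methods).** It repeats those purposes for the first 20 patients, labels the arms A and B, and says "all persons associated with the internal pilot study will be kept blinded for group assignment". Like Section 4.B, it mentions no efficacy or futility look.
- **Section 4.B (sample size).** "A sample size of n=52 per group will provide 80% power to detect a difference between the group means", the difference being -4.0 in ARI change with SD 7.2 in each arm. No early look is allowed for.
- **Section 12.B.** A third party applies the A/B labels in Section 12.F. Here there is also a "research pharmacist who will be un-blinded to each subject's treatment assignment".
- **Section 18.E.** To the question "Is there is an independent DSMB for this study" the answer is yes. A charter is to be submitted; it is not among the documents.

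**The concern.** A null-looking result in the first fifth of the trial becomes a reason to consider ending it for lack of efficacy, at a size chosen to estimate an SD. Three things follow.

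- Whoever applies the limb must choose the measure, the comparison and the cut-off after seeing data, and different choices can give different answers on the same 20 patients.
- If the limb is acted on, the trial has less than the 80% power stated in Section 4.B.
- The item heading speaks of irritability and of an effect of oxytocin, and its text has the study team (we) deciding. Section 12.F keeps pilot personnel blinded on a pilot of the same size, and Section 18.G names nobody else to do the judging.

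**Working it through.** **Inputs.** All come from Section 4.B unless noted: two-sided two-sample t-test at 0.05, mean change -4.0 on oxytocin and 0 on placebo, SD 7.2 in each arm, 52 per arm. The look at 10 per arm comes from Section 18.G. ARI change is used as the measure because it is the primary outcome; the no-change limb itself does not name it.

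**1. The plan's own figure.** Noncentral-t power for 4.0/7.2 is 80.1% at 52 per arm and 79.3% at 51. The stated 52 per arm reproduces.

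**2. Precision at 10 per arm.**
- SE of the difference = 7.2 × √(2/10) = 3.22.
- 95% half-width = 2.101 × 3.22 = 6.8. An observed difference of 0 has interval -6.8 to +6.8, which includes -4.0.
- The half-width is 0.94 × SD, so an observed zero would exclude -4.0 only if the SD were below about 4.3.
- Power for -4.0 is 21.8%.

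**3. Conditional power at 52 per arm after an observed difference of exactly 0.** With f = 10/52 = 0.192 and θ = 4/(7.2 × √(2/52)) = 2.833, CP = Φ[(Z₁√f + θ(1 − f) − 1.96)/√(1 − f)] with Z₁ = 0.
- If the design effect is true: (2.833 × 0.808 − 1.96)/0.899 = 0.365, so CP is about 64%.
- If there is no effect (θ = 0): −1.96/0.899 = −2.18, so CP is about 1.5%.

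**4. Illustration: no change taken as zero or worse, and always acted on.** This cut-off is an assumption; the plan gives none. It also takes in some results that the worsening limb would catch.

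| Reading | SE | Mean under design | Stop if drug works as assumed | Power at fixed 52 per arm |
|---|---|---|---|---|
| Oxytocin arm against baseline | 7.2/√10 = 2.28 | -4.0 | Φ(−4/2.28) = 3.9% | about 78% |
| Oxytocin against placebo | 3.22 | -4.0 | Φ(−4/3.22) = 10.7% | about 74% |
| All 20 pooled | 7.2/√20 = 1.61 | -2.0 | Φ(−2/1.61) = 10.7% | about 72% |

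The first two powers come from simulating the pilot and the final t-test. The pooled mean is independent of the between-arm difference, so its power is 0.801 × (1 − 0.107) = 0.715.

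The within-arm and between-arm readings trigger together 2.5% of the time under the design effect and 37.5% under no effect. Those two alone therefore disagree in 3.9 + 10.7 − 2 × 2.5 = 9.6% and 50 + 50 − 2 × 37.5 = 25% of pilots.

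**5. A looser cut-off.** If a between-arm benefit of 2 points or less counts as no change, the stop probability under the design effect is 26.7% and power falls to about 64% (normal approximation, 80.9% with no look).

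**6. Expected enrolment.** With no drug effect and zero placebo change, each zero-or-worse reading stops half the time: 104 − 84 × 0.50 = 62 patients, against 104 with no look. Under the design effect the early rule gives 104 − 84 × 0.039 = 100.7 or 104 − 84 × 0.107 = 95.0. These ignore dropout and patients enrolled while the pilot is read.

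**The case against.** The best case for the sponsor has five parts.

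- **The item says only consider.** That stands: the clause is discretionary, and an early exit for lack of efficacy does not inflate type I error. Discretion would reduce the losses above. It does not supply the missing measure or comparison, and the lead-in uses stronger language.
- **A strict reading is informative.** This stands in part. Zero or worse favours no effect over the design effect by 0.50/0.107 = 4.7 to 1 between arms and 0.50/0.0395 = 12.7 to 1 within the oxytocin arm, the latter only if placebo change is 0 as assumed. But an oxytocin-arm mean of exactly zero still has a half-width of 2.262 × 2.28 = 5.15, which includes -4.0.
- **Blinding need not be broken.** Also fair. Pooling all 20 needs no arm identity, and whether A and B differ can be seen from the labels. A reader might infer that the study team will be unblinded; the documents do not say so. Decoding is needed only for a judgement specific to oxytocin, which the item heading suggests but does not compel.
- **The DSMB charter may settle this.** It may, so one cannot say that the DSMB has no role. Section 18.G would still read as the team's own decision, and Section 18.H says investigators will closely monitor outcomes.
- **An early exit spares children in research rated greater than minimal risk.** This is a genuine trade-off and the main cost of the fix.

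A reader might also take no change to mean not statistically significant. That would stop an effective drug 65% (within arm) or 78% (between arms) of the time, but the text states no such test, so those figures are not relied on.

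**Conclusion.** The point holds as a defect in a discretionary stopping clause that should be fixed. The no-change limb is undefined, does not match the stated purpose of a pilot of the same size, and rests on a look with about 22% power that cannot exclude -4.0 after an observed zero.

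On the zero-or-worse illustration the cost, if acted on, is about 2, 6 or 8 points of power. Those are not general upper bounds, because a looser cut-off costs more. They assume SD 7.2, zero placebo change and a final size fixed at 52 per arm, although Sections 4.B and 12.F plan to recalculate that size from the pilot SD. The documents do not support saying that the rule is binding, that type I error is inflated, or that unblinding will occur.

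**What to change.** In Section 18.G:

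1. Delete the no-change (lack of efficacy) limb at 10 per arm and keep the pilot for SD, sample-size recalculation and retention, as Sections 4.B and 12.F say.
2. Keep the worsening limb, but state that any review of outcomes by arm is done by the independent DSMB and not the study team. Check that the charter agrees.
3. Reconcile the lead-in, which says the study would be halted, with the item, which says termination would be considered.

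This is a wording change and a charter check. The cost is losing a very early exit: expected enrolment if oxytocin has no effect rises from about 62 to 104 with no look.

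The sponsor may, as an option and not a required correction, add a later non-binding DSMB futility look with a stated conditional-power threshold. For example, at 26 per arm, stopping when conditional power under the design effect is below 20% (observed difference worse than about +0.15) stops 1.9% of the time if the drug works as assumed and 47% if it does not. Expected enrolment with no effect is then 104 − 52 × 0.47, about 80, and power changes by less than half a point at a fixed 52 per arm.

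If the early trigger is kept, state its measure, comparison and cut-off, and restate the power.
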